## 13. STUDY MEDICATION

### 13.1 Description of Study Medication

The study drug will be manufactured, packaged, and labeled under GMP.

VDA-1102 is formulated as a milky-white ointment, with the drug substance being dissolved in a water-free ointment base. There are no discernable differences in color between VDA-1102 ointment and placebo.

5% and 10% VDA-1102 topical ointments and placebo ointment are supplied in 10 gm aluminum tubes with plastic caps, and stored refrigerated at 2-8 °C (36-46°F). Placebo will be identical to VDA-1102 minus the API (Active Pharmaceutical Ingredient).

### 13.2 Drug Packaging

The study drug tubes are enclosed in an aluminum envelope with an enclosed desiccant. The pouch is packaged in a protective container.

### 13.3 Drug Labeling

Each tube will be labeled with the following information:

1. Study number
2. Name of the Sponsor
3. Drug name (or placebo)
4. Lot numbers for placebo, 5% VDA-1102, and 10% VDA-1102
5. Directions for use
6. The statement, "Caution: New drug - limited by United States law to investigational use"
7. Storage conditions (degrees C and F)
8. Quantity: 10 grams

### 13.4 Study Drug Distribution

Sites in the U.S. will receive their drug from a depot located in the United States, while sites located in Israel will receive their drug from an Israeli depot. Study drug will be shipped under refrigerated conditions with temperature loggers.

### 13.5 Study Drug Storage

#### *Site Pharmacy*

All study drug will be stored at the investigative site (or their institutional pharmacy) at 2-8 °C (36-46°F) in a secured area with access limited by coded keypads and/or locks.

#### *Home Storage*

Subjects will be instructed to keep the study drug tube in the accompanying container and to keep this unit in their home refrigerator.

### **Travel**

If a subject needs to transport the study drug (while travelling on vacation or business, or to the site), they will be instructed to protect the study drug from heat in the supplied cooler pack. The drug should not be placed in the trunk of a car or in checked luggage on a plane.

Subjects planning to travel away from home should contact their site in order to receive instructions how to properly care for the study drug.

## **13.6 Study Drug Dispensing and Administration**

### **13.6.1 Study Drug Dispensing**

Following conclusion of the Day 1 Pre-Dose procedures, the Investigator (or designee) will assure that the subject still meets all the study enrollment criteria. The investigator may then approve subject randomization.

Based on the randomization number generated by the IVRS, the site personnel (or institutional pharmacist) will allocate the appropriate study drug for each subject. The tube with its aluminum envelope will be removed from its container in the refrigerator. The envelope will be opened by site personnel and the tube removed. The aluminum envelope will be retained at the site for monitoring purposes and the tube will be placed in the container until dosing time.

### **13.6.2 Study Drug Dosing Cards**

Study Drug Dosing Cards will be distributed to all the sites. These cards will be used: (a) by site personnel to train and to test subjects in the proper length of the study drug ointment strip to be expressed and applied to the Treatment Field, and (b) by enrolled subjects to measure the appropriate length of study drug ointment to be applied each evening to their Treatment Field.

A sample of the Dosing Card is included in Section 22.6. Instructions regarding proper use of the Dosing Card are included in the Subject Instruction Sheet.

### **13.6.3 Study Drug Measurement and Application Review**

All sites will receive tubes of placebo with which to train all subjects to measure the appropriate quantity of study drug to be applied. These training tubes will be clearly marked.

Using the Treatment Field Template, placebo training ointment, and a Study Drug Dosing Card, the subject will be trained and tested in proper and precise dosing techniques.

**Note: Training tubes containing placebo ointment will only be used to practice measurement of the proper study drug dose on the Dosing Card and not for application to the face during training and testing.**

### ***Screening Visit***

Subjects will be trained and tested by site personnel at the Screening Visit. The subject will be taught to measure the study drug using placebo tubes supplied by the Sponsor. The subjects will also be taught how to apply the study drug, but they will not use the placebo for this part of the training. In other words, placebo should not be applied to their skin during the training.

Subjects who have difficulty measuring the dose or applying the study drug to the precisely may be asked to bring a dosing partner with them to the Day 1 Pre-Dose Visit. This dosing partner must be willing and able to assist the subject with study drug application once every evening for 28 days.

If the subject (or dosing partner) is unlikely to apply the study drug appropriately, the subject should be terminated from the study based on Inclusion#4 (Section 8.1).

### ***Day 1 Pre-Dose Visit***

Subjects who continue to meet the study enrollment criteria following Screening will be trained and tested twice by site personnel during the Day 1 Pre-Dose Visit: once at the beginning of the visit and once again at the end of the visit before randomization. If the subject (or dosing partner) is unlikely to apply the study drug appropriately, the subject should be excluded from the study based on Inclusion #4 (Section 8.1).

### ***Day 1 Dosing Visit***

Dosing at this visit will occur under the supervision of the site personnel. If at this visit the subject is unable to precisely prepare the study drug or is unable to properly locate the Treatment Field, they should be withdrawn before the study drug is applied. Application of the study drug during this visit will be the same as described in Section 13.6.4, below.

#### **13.6.4 Study Drug Administration at Home**

The study drug will be applied to the Treatment Field by the subject (or dosing partner) each evening approximately 2 hours before bedtime. If the subject would like to shower, wash their face, shampoo their hair, etc. before bedtime, these should be performed prior to study drug application.

At the dosing time, the subject should check the Treatment Field in the mirror to assure it is clean and dry.

The study drug tube will be removed from the container, the tube cover unscrewed, and the study drug ointment expressed as a strip into the rectangle printed on the supplied Dosing Card.

Using a mirror, photographs, and/or the landmarks drawn on the Treatment Field Template, the template will be appropriately positioned on the subject's face or scalp. The subject (or

dosing partner) will apply the study drug to the Treatment Field on their skin that corresponds to the 25 cm^2 area cut out of the template. Subjects (or their dosing partners) will apply the study drug with one finger to the center of the Treatment Field and spread the ointment evenly over the entire field. The Treatment Field will **not** be occluded. The subject will remove the Treatment Field Template from their face. With the same finger, the subject will spread ointment at the periphery of the Treatment Field approximately  $\frac{1}{4}$  inch beyond the Treatment Field perimeter in order to insure that the whole Treatment Field was covered with study drug.

The subject will be instructed not to wet or touch the Treatment Field from the time of dosing until the following morning.

### **13.7 Study Drug Accountability and Dosing Compliance**

The CRO will request the Investigator or their designee to sign a receipt for the study drugs on the day of arrival at the site. The site pharmacist and/or the assigned site personnel will be responsible for drug accountability. A drug accountability record should be maintained by the person responsible for dispensing the study drug to the subject. This should record which supplies arrived at the site and which container(s) is issued to each subject. The Medical Monitor should be notified of details of any supplies which are inadvertently damaged. Details of any supplies which are inadvertently damaged or unaccountable for any reason should be given on this drug accountability record, which will be collected at the end of the study.

All drugs will be inventoried by the monitor during and at the conclusion of the study. Secure disposal or return of unused supplies to the Sponsor at the end of the study will be arranged.

A single 10 mL tube of study drug will be assigned to each subject. Each tube will be weighed prior to the first dosing and at Day 7, 14, and 28 Visits. Subjects will also be asked during the once-weekly communication with the site and at each site visit whether they missed any doses and responses will be appropriately documented in the subject's medical record. In addition, subjects will complete a Dosing Diary, following each evening dose, with the date and time of dosing.

#### 14. CONCOMITANT MEDICATION

Any prescription or non-prescription medication, alternative medication, herbal product, homeopathic substance, etc. used by the subject from 30 days prior to Screening until the subject leaves the trial will be referred to as a Concomitant Medication. The Investigator is to record the use of all concomitant medications, both prescribed and over-the-counter, in the CRF.

Subjects should be advised against taking any new medication, both prescribed and over-the-counter, without consulting the Investigator, unless the new medication is urgently required for emergency use. Subjects taking medication other than those listed as prohibited in Section 12.6.1 may continue taking their routine medications and vitamins so long as they have been taking them for at least 2 months prior to Screening with no change in dose, manufacturer, or dosing interval.

At Screening and Day -1 Pre-Dose Visits, the study site personnel will check each subject's concomitant medications to ensure that subjects are not taking any prohibited medications listed in Section 12.6.1.

The Investigator and his designees are obligated to ensure the well-being of all subjects during this study. Consequently, no medication or treatment should be withheld from a subject requiring medical intervention. This may include treatments received by the subject prior to enrollment as well as in response to any new medical conditions that developed during the study. The Investigator (or designee) must inform a subject when concomitant medical intervention or treatment is indicated and report this in the appropriate section of the CRF.

## 15. ADVERSE EVENTS

### 15.1 Adverse Event Definition

An AE is any untoward medical occurrence in a subject administered a pharmaceutical product, which does not necessarily have to have a causal relationship with the pharmaceutical product treatment. Any worsening of the subject's disease under study or other medical conditions will also be considered to be an AE, unless it is within the normal range of disease fluctuation for that subject.

**In this trial LSRs will be collected independently of AEs. Any LSR that occurs within the selected Treatment Field and extends to adjacent surrounding skin (defined as within a 2 cm border around the Treatment Area) will be considered LSRs and will not be recorded as AEs. LSRs that require medical intervention (prescription medication) or extend beyond the 2 cm surrounding skin should be documented as an AE.**

Clinically meaningful (for a given subject) changes in physical examination and test findings should also be recorded as AEs. The criteria for determining whether an abnormal objective test finding should be reported as an AE are as follows:

1. Test result is associated with accompanying symptoms, and/or
2. Test result requires additional diagnostic testing or medical/surgical intervention, and/or
3. Test result leads to a change in study dosing or discontinuation from the study, significant additional concomitant drug treatment, or other therapy, and/or
4. Test result leads to any of the outcomes included in the definition of a SAE.

Merely repeating an abnormal test, in the absence of any of the above conditions, does not meet Condition 2 above for reporting as an AE.

Any abnormal test result that is determined to be an error does not require reporting as an AE.

Treatment Emergent Adverse Events (TEAEs) are AEs that occur *de novo* or worsen following the initiation of study treatment.

Surgical procedures themselves are not AEs; they are therapeutic measures taken for the AE, and should be documented as such.

Planned hospital admissions documented in the subject's CRF prior to randomization and study-related procedures are also not AEs.

Overdoses of the study drug will not be reported as an AE. However, any AEs or SAEs, as defined in Section 15, associated with an overdose will be reported as such.

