## 7.5 Safety Reporting

### 7.5.1 Expedited Reporting to Sponsor and CRO

In addition to the reporting requirements for serious adverse events (SAEs) described in Section 16, all severe AEs must be reported to the Study Medical Monitor and the site's CRO contact within 24 hours.

All dose holidays and adjustments (described in Section 7.6 below) must be reported to the Study Safety Monitor (Sponsor) and the site's CRO contact within 24 hours. Such occurrences must be documented in the eCRF along with the reason for their occurrence.

In addition, if at any time during the course of the trial a potentially serious safety finding is noted by an Investigator, the Sponsor's Study Medical Monitor and the site's CRO contact must be notified within 24 hours.

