#### **10.1.6 Once-Weekly Subject Contact**

Site personnel will contact each subject once-weekly during the Treatment Period. The goals of this contact are: (a) to review the Dosing Instruction Packet and Dosing Diary with each subject; (b) to answer any questions raised by the study participants; (c) to remind subjects of their upcoming site visit and any related activities; and (d) to remind subjects to bring their study drug to each site visit.

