## 22. APPENDICES

### 22.1 Local Skin Reaction Score

This score has been modified from a score published in Lebwohl M et al (2012), “Ingenol Mebutate Gel for Actinic Keratosis”, *N Engl J Med* 2012;366:1010-9).

The Local Skin Reaction Score is an assessment of all the skin in the Treatment Field (not of the AK lesions). At each study visit the Investigator (or designee) will assign a severity score to each of the objective and subjective findings listed in the table. For example, if the Treatment Field contains vesicles of moderate severity, the number 3 would be placed under the field labelled “Vesicles”.

[figure not shown]
The Investigator will assess the selected Treatment Field and rate the findings on a 5 point scale. The LSR score will consist of the sum of all the individual severity scores.

Treatment Field Findings	Erythema	Edema	Weeping or Exudate	Vesicles	Erosion or Ulceration	Scaling or Dryness	Scabbing or Crusting	Itching	Pain
Severity Score									

The 5 point LSR Score is: **0 = No reaction, 1=Trace reaction, 2= Mild reaction, 3=Moderate reaction, and 4=Severe reaction.**

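### The AE exemption for local skin reactions reaches 2 cm past the Treatment Field, but the LSR score stops at the field edge, so the border part of a reaction is ungraded although some of that skin is dosed

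*Protocol*

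**What the plan says.** Four parts of the protocol bear on this.

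- **AE rule (15.1).** LSRs are collected separately from AEs. The exemption opens with "Any LSR that occurs within the selected Treatment Field and extends to adjacent surrounding skin". The same sentence sets the border width and the consequence: "adjacent surrounding skin (defined as within a 2 cm border around the Treatment Area) will be considered LSRs and will not be recorded as AEs". The next sentence restores two cases: "LSRs that require medical intervention (prescription medication) or extend beyond the 2 cm surrounding skin should be documented as an AE".
- **Scored area (10.1.5 and 22.1).** "The Local Skin Reaction Score is an assessment of all the skin in the Treatment Field (not of the AK lesions"). Each component is rated 0 to 4. The form in 22.1 has one cell per finding and none for skin outside the field or for extent of spread.
- **Dosed area (13.6.4, repeated in 22.7 and 22.8).** After removing the template, "the subject will spread ointment at the periphery of the Treatment Field approximately" 1/4 inch past its perimeter.
- **Other records.** Physical examinations include the skin, and abnormal findings must be recorded (9.4.3). Section 15.1 also makes clinically meaningful examination changes AEs. Dose holidays and adjustments are reported within 24 hours, with the reason entered in the eCRF (7.5.1).

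The SAP (5.6.7.3) analyses the composite LSR score and its components. It defines no variable for border skin.

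**The concern.** The protocol takes local reactions out of the AE record on the understanding that a dedicated instrument records them instead. That works only if the instrument covers at least the area that has been exempted. Here it does not: the exemption runs 2 cm past the field, the score stops at the field edge, and dosing crosses that edge.

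Local skin safety and tolerability is a secondary objective (section 6), and section 5.3 presents the lack of necrosis and inflammation as the drug's advantage over existing field treatments. The blinded Day 7 review of the first 15 subjects (7.3) names AEs, LSR scores, laboratory results and ECGs. Under the LSR rule, spread into the border enters neither of the two streams there that bear on skin. The SAP cannot recover it, because no graded border data would exist.

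Two related gaps follow from the same rule. Among the AE criteria in 15.1 is "Test result leads to a change in study dosing or discontinuation from the study", but no matching trigger exists for a skin reaction that changes dosing. And the goals of the weekly call, which begin "The goals of this contact are: (a) to review the Dosing Instruction Packet and Dosing Diary with each subject", do not include asking about skin reactions.

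**Working it through.** The documents give no figure on this point, so there is none to reproduce. The check compares coverage rule by rule and then sizes the uncovered area.

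**Coverage of a reaction that starts in the field and spreads into the border, needs no prescription medication and stays within 2 cm**

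| Part of the reaction | LSR grade (10.1.5, 22.1) | AE under the LSR rule (15.1) |
|---|---|---|
| Inside the field | Yes, 0 to 4 | No |
| Dosed ring, 0 to about 0.6 cm outside | No | No |
| Rest of the border, to 2 cm | No | No |

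A reaction confined to the border is a separate case. The exemption describes reactions that occur in the field and extend outward, so the general AE definition may apply to it. The text does not settle this.

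**Inputs for the area.** The field is 25 cm2 (13.6.4). A square or rectangle is recommended (11.1.3). The spread is m = 2.54/4 = 0.635 cm (13.6.4) and the border is m = 2 cm (15.1). The side lengths a and b are my assumption, so three shapes are shown.

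**Formulas.** Ring with rounded corners: 2(a+b)m + pi x m^2. Ring with square corners: (a+2m)(b+2m) - ab.

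For 5 x 5 cm and m = 0.635:
- rounded: 20 x 0.635 + 3.1416 x 0.403 = 12.70 + 1.27 = 13.97 cm2
- square: 6.27^2 - 25 = 39.31 - 25 = 14.31 cm2
- share of all dosed skin: 13.97/38.97 = 35.8% to 14.31/39.31 = 36.4%

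| Field (cm) | Dosed ring (cm2) | Share of dosed skin | Full 2 cm border (cm2) |
|---|---|---|---|
| 5 x 5 | 13.97 to 14.31 | 35.8 to 36.4% | 52.57 to 56.00 |
| 4 x 6.25 | 14.28 to 14.63 | 36.4 to 36.9% | 53.57 to 57.00 |
| 2.5 x 10 | 17.14 to 17.49 | 40.7 to 41.2% | 62.57 to 66.00 |

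For the 5 x 5 cm field, the dosed ring is about a quarter of the AE-exempt border (13.97/52.57 = 27%; 14.31/56 = 26%). The rest of the border is not deliberately dosed.

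**Completeness of the other records.** The visit lists in 12.4 schedule a physical examination for all subjects on Days 14, 28 and 35. On Day 7 it is for the first 15 subjects only. The Day 56 and Day 84 lists contain none, although protocol Table 5 appears to tick Day 56. None of these examinations yields a 0-4 border grade. Section 15.1 holds both the LSR exemption and the rule on clinically meaningful examination changes, and does not say which governs when both apply.

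**The case against.** The strongest reply is that keeping LSRs apart from AEs is a deliberate, emphasised choice with its own SAP analysis, and that the uncovered part is small. A reaction that starts in the field is scored there at each visit, so its occurrence is not lost; only its extent is. The ring receives only what the same finger carries outward after the field is dosed, and nothing in the documents suggests reactions arising on the ring alone. Further AE reporting detail sits in a Safety Monitoring Plan that is not among the documents (15.3). All of this is fair, and it limits the point to a mismatch of areas.

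Four stronger readings might be inferred. The documents do not support them.

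- **That border reactions are captured nowhere.** Skin examinations on Days 14, 28 and 35, the AE rule for clinically meaningful examination changes, and dose-holiday reasons in the eCRF all provide partial records. The SAP (5.6.7.5) summarises examinations and dosing adjustments.
- **That about 36% of reactions are missed.** That figure is an area share under an assumed square field. The documents give no event rate for the ring.
- **That the medical monitor hears late of severe reactions.** Section 7.5.1 already requires a 24-hour report of any dose holiday or adjustment, and of any potentially serious finding. What is left is a score-4 LSR with no dosing change, no prescription medication, no spread past 2 cm and no judgement that it is potentially serious. Calling it an AE would not by itself bring it under "all severe AEs must be reported to the Study Medical Monitor and the site's CRO contact within 24 hours", because 15.2 defines a severe AE by inability to work or carry out normal daily activity, not by an LSR score.
- **That a reaction peaking between Day 14 and Day 28 leaves no record.** That interval is 14 days nominally, and 20 at the window extremes (Day 12 to Day 32). Within it, missed doses are asked about weekly and documented (13.7), subjects can raise questions, and unscheduled visits are possible (12.5). A mild reaction with no consequence could go unrecorded, but that concerns visit frequency rather than the border.

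**Conclusion.** The mismatch is real and should be corrected, in a limited form. For a reaction that spreads from the field into the 2 cm border without needing prescription medication, the border part has no 0-4 grade and no AE entry under the LSR rule. About 14 cm2 of that border is deliberately dosed for a 5 x 5 cm field, and 14 to 17.5 cm2 across the three rectangles tried. Other records pick it up only partly and ungraded, and 15.1 leaves open which of its own two rules prevails, so sites may record the same reaction differently.

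This rests on reading 10.1.5 and 22.1 literally as field-only, on the assumed field shapes, and on the Safety Monitoring Plan not already closing the gap. It affects the completeness of a secondary safety objective. It does not show that reaction incidence is undercounted by any stated amount, and it does not touch the primary endpoint.

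**What to change.** 1. In 10.1.5 and 22.1, score the 2 cm border on a separate row of the existing LSR form, so that the scored area matches the AE-exempt area. Summarise that row separately in the SAP, so the field score stays comparable with data already collected.
2. In 15.1, state which rule prevails when an exempt LSR is also a clinically meaningful examination change, and how a reaction confined to the border is recorded.
3. In 15.1, record as an AE any LSR that leads to a dose holiday, adjustment or stop, so that AE tables show it. The 24-hour report in 7.5.1 already covers these cases; this changes recording, not management.
4. If prompt notice of a score-4 LSR is wanted, say so directly in 7.5.1 rather than relying on AE severity, which uses a different scale.
5. Add one question on skin reactions to the weekly call in 10.1.6.

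The cost is protocol wording, one form row, one question in a call already made and one extra summary. The downside is slightly more recording and somewhat more AEs listed.
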